10.3.1.1 Overview of TEAEs

An overview table of TEAEs will be provided with the following categories:

- Number of TEAEs (total number of TEAEs)
- Subjects with any TEAEs
- Subjects with TEAEs by strongest relationship
- Subjects with TEAEs by maximum severity
- Subjects with related TEAEs
- Subjects with Grade 3/4 TEAEs
- Subjects with serious TEAEs
- Subjects with related serious TEAEs (possibly related, related or missing)
- Subjects with TEAEs leading to treatment discontinuation
- Subjects with TEAEs leading to treatment interruption
- Subjects with TEAEs leading to death

The frequency counts and percentages will be presented for the above overview table. Exposure adjusted event rates may also be provided.

In addition, listings containing individual subject adverse event data for TEAEs leading to treatment discontinuation, treatment interruptions, SAEs and all deaths will be provided separately, with a flag indicating the TEAE status for SAEs and deaths.

10.3.1.2 TEAEs by SOC and PT

The following summary tables of TEAEs will be provided:

- All TEAEs
- Related TEAEs
- Grade 3/4 TEAEs
- Serious TEAEs
- Related Serious TEAEs (possibly related, related or missing)
- TEAEs by strongest relationship
- TEAEs by maximum severity

- TEAEs leading to treatment discontinuation
- TEAEs leading to treatment interruption
- TEAEs leading to death

Summaries will be presented by MedDRA SOC and PT using frequency counts and percentages (i.e., number and percentage of subjects with an event). For selected summary tables, the exposure adjusted event rate may also be provided.

When summarizing the number and percentage of subjects with an event, subjects with multiple occurrences of the same AE or a continuing AE will be counted once; only the maximum severity level will be presented in the severity summaries and the strongest relationship level will be presented in the relationship summaries. While summarizing the number of events for the exposure adjusted even rate, all occurrences will be counted.

10.3.1.3 TEAEs and SAEs by PT

The number and percentage of subjects with TEAEs and SAEs will be summarized by PT. Exposure adjusted event rates may also be provided. When summarizing the number and percentage of subjects with an event, multiple occurrences of the same adverse event or a continuing adverse event for the same subject will be counted once. While summarizing the number of events for the exposure adjusted event rate, all occurrences will be counted.

10.3.1.4 TEAEs of Special Interest

For treatment-emergent elevated transaminase events, respiratory symptoms, and respiratory events (PT lists are provided in

[Appendix H](#)), the following categories will be summarized in terms of frequency counts:

- Subjects with events
- Subjects with events by maximum severity
- Subjects with events leading to treatment discontinuation
- Subjects with events leading to treatment interruption
- Subjects with serious events
- Subjects with related serious events
- Subjects with events leading to death
- Duration of events
- Time-to-onset of first event

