5 INTRODUCTION

5.1 Background

Cystic fibrosis (CF) affects an estimated 70,000 children and adults worldwide.¹ CF is a progressive, systemic, life-shortening, genetic disease that is caused by reduced quantity and/or function of the CFTR protein due to mutations in the *CFTR* gene. In people with CF, loss of chloride transport due to defects in CFTR result in the accumulation of thick, sticky mucus in the bronchi of the lungs, loss of exocrine pancreatic function, impaired intestinal absorption, reproductive dysfunction, and elevated sweat chloride concentration. Lung disease is the primary cause of morbidity and mortality in people with CF. The median predicted age of survival of individuals born today with CF is approximately 40 years of age.^{1,2}

Two complementary approaches to increase CFTR-mediated Cl⁻ secretion in the airway epithelia have been studied.³ One approach is to treat with a compound that will modify the cellular processing and trafficking of the CFTR protein to increase the amount of functional CFTR at the cell surface. This kind of compound has been termed a CFTR corrector. Another approach is to treat with a compound that increases the channel gating activity of CFTR at the cell surface to enhance ion transport. This kind of compound has been termed a potentiator.

Tezacaftor (TEZ) and ivacaftor (IVA) are CFTR modulators with interdependent mechanisms of action in treating CF patients with CFTR mutations that require a combination therapy approach. TEZ and IVA both address the underlying cause of CF, and each has a different and essential role as a corrector (TEZ) or potentiator (IVA) of the CFTR protein in CF patients.

TEZ (VX-661) and IVA (VX-770) were developed by Vertex Pharmaceuticals Incorporated (Vertex). TEZ/IVA combination therapy (trade names Symdeko™ and Symkevi™) is indicated for the treatment of CF in patients as young as 6 years of age homozygous for *F508del* or who have another indicated *CFTR* genotype. IVA monotherapy (Kalydeco™) is indicated for the treatment of CF in patients as young as 2 years old with specific *CFTR* mutations including certain gating mutations as well the *R117H* mutation. The indicated mutations and approved populations for Symdeko/Symkevi and Kalydeco vary by country. Please refer to local prescribing information or summary of product characteristics for your region for the current approved use of Symdeko/Symkevi and Kalydeco.

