9.9 Discontinuation of Study Participation

If after review of a marketing application, local health authorities decline to approve TEZ/IVA for the treatment of CF in a corresponding population aged ≥ 12 years, pediatric subjects enrolled in Study 116 with the relevant *CFTR* genotypes may be discontinued after communication to investigators and IRBs/IECs of the risks/benefits related to the safety and efficacy observed for the subset of subjects. In addition, if evaluation of efficacy data from Phase 3 Study VX14-661-110 suggests that the TEZ/IVA treatment does not provide clinically meaningful benefit for a population enrolled in Study 116, Vertex may recommend that subjects with relevant *CFTR* genotypes discontinue the study.

Subjects who become eligible to receive commercially available TEZ/IVA by prescription of a physician may be discontinued from this rollover study at the discretion of the sponsor. The timing of assessments after study discontinuation is described in Section 9.1.2 and Section 9.1.3.

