8 ANALYSIS SETS

The following analysis sets are defined for Study 116 Part A: All Subjects Set, Safety Set, Full Analysis Set, 113B/116 Full Analysis Set, 115/116 Full Analysis Set, and 113B/116 LCI Full Analysis Set.

Enrolled subjects are those who signed a consent/assent form and had an enrollment date in the CRF for Part A.

All Subjects Set

The **All Subjects Set** will be defined as all subjects who were enrolled in Study 116 Part A or received at least 1 dose of TEZ/IVA in Study 116 Part A. This analysis set will be used for all individual subject data listings and the disposition summary table, unless specified otherwise.

Full Analysis Set (FAS)

The **Full Analysis Set (FAS)** will be defined as all subjects who were enrolled in Study 116 Part A, who received at least 1 dose of TEZ/IVA in Study 116 Part A and have an eligible genotype. The FAS will be used for efficacy analyses, unless otherwise specified.

115/116 Full Analysis Set (FAS), 113B/116 FAS and 113B LCI/116 FAS

The 115/116 FAS will be defined as the subset of FAS who were enrolled in parent Study 115. The 113B/116 FAS will be defined as the subset of FAS who were enrolled in parent Study 113B. The 113B/116 LCI FAS will be defined as the subset of Study 113B subjects who participated in the LCI sub-study in Study 113B.

Safety Set

The **Safety Set** will be defined as all subjects who are enrolled in study 116 Part A and who received at least 1 dose of TEZ/IVA in Study 116 Part A. The Safety Set will be used for all safety analyses, unless otherwise specified.

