10.3.2 Clinical Laboratory Values

For laboratory measurements, the raw values and change from treatment baseline values of the continuous hematology, chemistry, vitamin, and lipids results will be summarized in SI units at each scheduled time point in the TE period based on the Safety Set.

The number and percentage of subjects with laboratory measurements meeting threshold criteria during the TE period will be summarized based on the Safety Set for selected laboratory measurements.

The threshold criterion shift from treatment baseline during the TE period will also be summarized for selected LFT laboratory parameters. The threshold criteria are provided in [Appendix G](#).

A listing of subjects with elevated LFT results during the TE period will be presented based on any of the following: AST $>3 \times$ ULN, ALT $>3 \times$ ULN, GGT $>3 \times$ ULN, ALP $>3 \times$ ULN, or total bilirubin $>2 \times$ ULN. For each subject in the listing, LFT assessments at all the time points will be included (scheduled and unscheduled).

In addition, a listing containing individual subject hematology and chemistry values outside the normal reference ranges will be provided. This listing will include data from both scheduled and unscheduled visits.

Only central lab results will be used for the tables. Local lab results will be included in the listings.

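### Special-interest AE counts and laboratory-threshold percentages take no account of unequal follow-up, so they would understate 96-week cumulative risk if a material share of subjects leaves early

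*SAP*

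**What the plan says.** **Special-interest events.** SAP 10.3.1.4 covers elevated transaminases, respiratory symptoms and respiratory events: "the following categories will be summarized in terms of frequency counts". The list ends with duration and "Time-to-onset of first event", but gives no censoring rule, risk set or cumulative-incidence estimate.

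**Laboratory thresholds.** SAP 10.3.2: "The number and percentage of subjects with laboratory measurements meeting threshold criteria during the TE period will be summarized based on the Safety Set". No exposure-adjusted version is offered. SAP 8 puts everyone enrolled and dosed in that set, however long they were followed: "The Safety Set will be used for all safety analyses, unless otherwise specified".

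**Early exit.** Protocol 9.9: "Subjects who become eligible to receive commercially available TEZ/IVA by prescription of a physician may be discontinued from this rollover study". Protocol 5.1 says the combination "is indicated for the treatment of CF in patients as young as 6 years of age", with approved populations differing by country. Exclusion criterion 6 (Protocol 8.2) lets a subject leave for another study by the same sponsor. Under Protocol 13.1.1.3, AE collection stops at the ETT Visit for those who move to commercial or managed-access drug.

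**Exposure adjustment elsewhere.** SAP 10.3 commits to exposure-adjusted rates where Study 116 AE data stand beside pooled parent-study data. In SAP 10.3.1.1 they are optional ("Exposure adjusted event rates may also be provided"), as they are in 10.3.1.2 and 10.3.1.3. The last two sections count all occurrences in the rate. SAP 10.2.5 reports total patient-years and 12-week exposure categories.

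**The concern.** The primary objective is long-term safety, and SAP 4 describes Part A as evaluating 96 weeks of treatment. A child released at Week 24 without an event stays in the Safety Set and looks the same as a child followed event-free to Week 96. Where such exits are common, a count or a fixed-denominator percentage falls below the proportion who would have had an event over 96 weeks.

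Elevated transaminases matter most here. The SAP makes them an event of special interest, and Protocol 11.4.3 ties ALT and AST levels to interruption of study drug. A reader of a 96-week safety report may well take the tabulated percentage as the 96-week risk.

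**Working it through.** **The plan's own figure.** The only size figure is the maximum number eligible: 56 from Study 113B + 65 from Study 115 = 121, as the protocol synopsis states. There is no planned event rate, 96-week risk, power or early-exit share to reproduce.

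**Inputs.** From the documents: N = 121 at most; treatment to Week 96; TE period ending at the earlier of 28 days after last dose and end of participation (SAP 9.1). Assumed: R, the true 96-week first-event risk (5% to 30%); s, the share leaving early (10%, 25%, 50%); t, the week their observation ends (24, 48, 72).

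**Formula.** Under a constant hazard, risk by week t is 1 − (1 − R)^(t/96), so the expected crude proportion is

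(1 − s)·R + s·[1 − (1 − R)^(t/96)].

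**Worked case.** R = 20%, s = 25%, t = 48:
- risk by Week 48 = 1 − 0.80^0.5 = 10.6%
- crude = 0.75 × 20% + 0.25 × 10.6% = 17.6%
- 121 × 0.176 = 21.3 subjects with an event, against 121 × 0.20 = 24.2
- relative shortfall 11.8%, or 2.4 percentage points

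A simulation of this case (N = 121, 4,000 runs) gave a mean crude proportion of 17.7%. Kaplan-Meier at Week 96 gave 20.0%, and so did the first-event rate converted to 96 weeks.

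**Relative shortfall, R from 5% to 30%, follow-up cut at Week 96:**

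| Share leaving | at Week 72 | at Week 48 | at Week 24 |
|---|---|---|---|
| 10% | 2.2–2.5% | 4.6–4.9% | 7.2–7.5% |
| 25% | 5.4–6.1% | 11.4–12.3% | 17.9–18.6% |
| 50% | 10.9–12.3% | 22.8–24.7% | 35.8–37.3% |

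With exits spread evenly over 0 to 96 weeks, the shortfall is about 5%, 12% and 24% for the three shares.

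**Two variants that shrink it.**
- *Early events.* If 70% of events occur by Week 24 and the rest evenly afterwards, the shortfall is 1–3%, 2.5–7.5% and 5–15% for the three shares (R = 10% or 20%).
- *Observation past Week 96.* A completer with a Safety Follow-up Visit can be observed to about Week 96 + 28/7 = 100. If every completer is, and nobody leaves early, the crude proportion exceeds the 96-week risk by 3–4% relative. For R = 20%: 1 − 0.80^(100/96) = 20.7%. The net effect then becomes understatement only when s passes about 5% (exit at Week 24), 7–8% (Week 48) or 14% (Week 72).

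**Against sampling error.** At R = 20% and N = 121, the standard error is √(0.20 × 0.80/121) = 3.6 points, so the 95% half-width is about 1.96 × 3.6 = 7.1 points. The worked shortfall of 2.4 points is smaller than this, but it is systematic.

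**The case against.** A reader might infer that the plan understates 96-week risk outright. The documents do not support that. Exit is permitted, not required. Availability varies by country. SAP 9.1 also provides for subjects who complete Part A and only then move to Part B or commercial drug, with full follow-up to Week 96. No early-exit share is given, and with near-complete retention the sign can reverse slightly. Nor does any section call these figures a 96-week risk. As counts of what was observed they are correct, and all safety summaries are descriptive.

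A reader might also infer that unequal follow-up is ignored. It is not. Besides the rates committed in SAP 10.3, the plan reports patient-years, exposure categories, discontinuations with reasons, and a listing of every subject with ALT or AST >3×ULN. With at most about 121 subjects, individual review is feasible.

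What these provisions leave open is narrower:
- SAP 10.3 does not say whether its commitment reaches the special-interest tables, and it concerns AE data, not laboratory thresholds.
- Rates that count all occurrences do not give the share of children affected, since one child with recurrent events raises the rate.
- Total patient-years cannot yield a first-event rate, which needs each subject's time cut at the first event.
- A listing of cases shows nothing about time at risk among subjects without an event.

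Kaplan-Meier has limits too. It assumes that stopping is unrelated to risk, which is doubtful for exits for safety or lack of benefit. Subjects also enter with different prior exposure: Study 113B subjects after its Week 24 Visit, and Study 115 subjects after its Week 8 Visit, where only some were randomized to TEZ/IVA.

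**Conclusion.** The point holds conditionally and is a cheap improvement, not a flaw that invalidates the safety analysis. If a material share stops before Week 96, the crude figures would understate cumulative risk over the treatment period by about 2–7% relative with 10% leaving, 5–19% with 25% and 11–37% with 50%. That rests on a constant hazard, exits unrelated to event risk, and follow-up cut at Week 96. Early events shrink the effect, and near-complete retention removes it.

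The gap is clearest for laboratory thresholds, which have no exposure-adjusted option. Two readings of the text remain open: whether the SAP 10.3 rates extend to the special-interest tables, and whether the laboratory percentage divides by the whole Safety Set, which its wording suggests but does not state.

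**What to change.** Keep the planned counts and percentages. For each special-interest TEAE group, and for first ALT or AST >3×ULN, add to SAP 10.3.1.4 and 10.3.2:

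- a first-event incidence rate per 100 patient-years, with time cut at the first event or the end of the TE period;
- Kaplan-Meier cumulative incidence at Weeks 24, 48 and 96, with numbers at risk and 95% CI, time running from the first Study 116 dose;
- both overall and by parent study, because prior TEZ/IVA exposure differs.

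In the disposition table, report administrative exits (commercial drug, managed access, another study) separately from exits for safety or lack of benefit, so that the assumption of non-informative stopping can be judged.

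The cost is a few table rows from dates already collected. The downsides are wide late intervals, especially by parent study, and the reliance of Kaplan-Meier on non-informative stopping. At a 20% risk with full follow-up, the 95% half-width is already about 1.96 × √(0.16/56) = 10.5 points for 56 subjects and 1.96 × √(0.16/65) = 9.7 points for 65.

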10.3.2 Clinical Laboratory Values

For laboratory measurements, the raw values and change from treatment baseline values of the continuous hematology, chemistry, vitamin, and lipids results will be summarized in SI units at each scheduled time point in the TE period based on the Safety Set.

The number and percentage of subjects with laboratory measurements meeting threshold criteria during the TE period will be summarized based on the Safety Set for selected laboratory measurements.

The threshold criterion shift from treatment baseline during the TE period will also be summarized for selected LFT laboratory parameters. The threshold criteria are provided in [Appendix G](#).

A listing of subjects with elevated LFT results during the TE period will be presented based on any of the following: AST $>3 \times$ ULN, ALT $>3 \times$ ULN, GGT $>3 \times$ ULN, ALP $>3 \times$ ULN, or total bilirubin $>2 \times$ ULN. For each subject in the listing, LFT assessments at all the time points will be included (scheduled and unscheduled).

In addition, a listing containing individual subject hematology and chemistry values outside the normal reference ranges will be provided. This listing will include data from both scheduled and unscheduled visits.

Only central lab results will be used for the tables. Local lab results will be included in the listings.

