^o Vital signs and pulse oximetry will be collected before dosing and after the subject has been at rest for at least 5 minutes.

^p The MBW assessment will be performed on multiple replicates and before study drug dosing (see Section 11.3.1 and the Study Reference Manual). MBW should be performed pre-bronchodilator [REDACTED]

^r Blood samples should be collected before the first dose of study drug on Day 1. Blood sampling for all other clinical visits except the Day 1 Visit may be conducted at any time after the ECG assessment and before the snack or meal.

Table 3-1 Study VX17-661-116: Treatment Period and Safety Follow-up Visit

Event/Assessment ^a	Treatment Period			Weeks 12, 24, 36, 48, 60, 72, 84, and 96 (±7 days)	ETT Visit ^{b,c}	Safety Follow-up Visit 28 (±7) Days After Last Study Drug Dose ^{b,c}
	Day 1 ^d	Study 115 Subjects Only				
		Day 15 (± 3 days)	Week 4 (±7 days)			
Sweat chloride ^t	X			Weeks 24, 48, and 96	X	
Meal(s) or snack(s) at site ^v	X	X	X	X ^w		
Study drug count		X	X	X	X	
Study drug dosing ^x	Day 1 to Week 96					
Medications review	Continuous from signing of the ICF and assent (where applicable) through the Safety Follow-up Visit					
Treatment and procedures review	Continuous from signing of the ICF and assent (where applicable) through the Safety Follow-up Visit					
AEs and SAEs ^y	Continuous from signing of the ICF and assent (where applicable) through the Safety Follow-up Visit					

AE: adverse event; BMI: body mass index; CF: cystic fibrosis; CFQ-R: CF Questionnaire–Revised; ETT: Early Treatment Termination; ICF: informed consent form; IVA: ivacaftor; LCI: lung clearance index; MBW: multiple-breath washout; SAE: serious adverse event; TEZ: tezacaftor

^t No other assessments should overlap with sweat chloride collection.

^v A fat-containing meal or snack will be provided at the site to subjects after all predose assessments have occurred.

^w Providing a meal or snack is optional at the Week 96 Visit.

^x The study drug should be administered every 12 hours (± 2 hours) within 30 minutes after starting a meal with fat-containing food. On days of scheduled visits, the morning dose of study drug will be administered at the site after the predose assessments have been completed. The final dose of study drug will be administered the evening before the Week 96 Visit.

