9.1 Study 116 Analysis Periods

The Safety analysis period is defined as the **treatment emergent (TE) Period**. The safety analysis period begins at the first dose of study drug in Study 116 Part A and ends 28 days after the last dose of study drug in Study 116 Part A, or at the date of Study 116 Part A participation completion, whichever occurs first.

The safety analyses will be performed on the Safety Set over the Safety Analysis Period, unless otherwise specified.

Safety and tolerability will be assessed by clinical review of all relevant parameters including AEs, Physical Exams, ophthalmologic examinations, clinical laboratory values, vital signs, ECG measurements, and pulse oximetry.

Only descriptive summaries will be presented, and no statistical testing is planned.

Completion of study participation in Study 116 Part A is defined as one of the following:

- For subjects who complete Study 116 Part A and do not roll over to Part B: The Safety Follow-up Visit
- For subjects who complete Study 116 Part A and roll over to Part B or transition to Commercial Drug: The Week 96 Visit
- For subjects who prematurely discontinue study drug treatment but do not withdraw consent in Study 116 Part A: the latest of early treatment termination (ETT) Visit, or Safety Follow-up Visit (if applicable)
- For subjects who withdraw consent in Study 116 Part A: date of withdrawal of consent
- For subjects who are lost to follow-up in Study 116 Part A: the date of last contact

The efficacy analysis period begins at the first dose of study drug in Study 116 Part A and ends at the last study visit at which efficacy data are collected in Study 116 Part A as described in the visit window in the Appendix A. The efficacy analysis will be performed on all subjects in the FAS by parent study for the efficacy analysis period, unless specified otherwise.

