10 STATISTICAL ANALYSIS

10.1 General Considerations

The Schedule of Assessments is provided in the clinical study protocol (CSP) Table 3-1. The precision standards for reporting safety and efficacy variables are provided in an internal Biometrics document that specifies the programming rules including the precision for derived variables.

All individual subject data for subjects who were enrolled in a parent study and who received at least 1 dose of TEZ/IVA in either parent study or in Study 116 will be presented in individual subject data listings.

Continuous variables will be summarized using the following descriptive summary statistics: the number of subjects (n), mean, standard deviation (SD), median, minimum value (min), and maximum value (max).

Categorical variables will be summarized using counts and percentages. Percentages will be presented to 1 decimal place.

Day 1, unless specified otherwise, will be defined as the day of the first dose of TEZ/IVA, in the Study 116 Part A.

Baseline value for safety analysis will be defined as the most recent non-missing measurement (scheduled or unscheduled) collected before the first dose of TEZ/IVA, whether the first dose was taken in the parent study or in Study 116 Part A. For ECGs, the baseline value will be defined as the last non-missing measurement (scheduled or unscheduled) before the first dose of TEZ/IVA or the average of measurements (triplicate) before the first dose of TEZ/IVA, whether the first dose was taken in the parent study or in Study 116 Part A.

Baseline value for efficacy analysis will be defined as the same as baseline of the parent study.

Change (absolute change) from baseline will be calculated as $\frac{\text{Post-baseline value} - \text{Baseline value}}$.

Relative change from baseline will be calculated and expressed in percentage as $\frac{100\% \times (\text{Post-baseline value} - \text{Baseline value})}{\text{Baseline value}}$.

The data from Study 116 will be integrated with data from the parent studies for the purpose of providing robust safety and efficacy analyses.

Unscheduled visits: Unscheduled visit measurements will be included in analysis as follows:

- In scheduled visit windows per specified visit windowing rules.
- In the derivation of baseline measurements.
- In the derivation of maximum/minimum values and maximum/minimum change from baseline values for safety analyses.
- In individual subject data listings as appropriate.

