10.3 Safety Analysis

The primary objective of Study 116 Part A is to evaluate the long-term safety and tolerability of TEZ/IVA. The overall safety profile of study drug will be assessed in terms of the following safety and tolerability endpoints:

- Treatment-emergent adverse events (TEAEs)
- Clinical laboratory values
- Standard 12-lead ECGs
- Vital signs
- Pulse oximetry
- Ophthalmologic examination

Analysis of AEs will be based on events that occur during the TE period of the Part A, for all subjects in the Safety Set. Pooled AE data from Study 113 Part B and Study 115 (only those who received TEZ/IVA) will be displayed side-by-side with AE data from Study 116 Part A. When displayed side-by-side with parent study results, exposure-adjusted rates will be provided.

Other safety analyses will be based on data from the TE period for all subjects in the Safety Set; and will be presented overall. The Safety Set will be used for all listings unless otherwise specified.

Baseline value will be used to calculate change from baseline for continuous safety endpoints.

Only descriptive summaries will be presented, and no statistical testing is planned.

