| | | 116A Week 48 | 337 | (295, 379] | |
| | | 116A Week 60 | 421 | (379, 463] | |
| | | 116A Week 96 | 673 | (631, 687] | |

| | | | | |
|--|--|--------------|-----|------------|
| | | 116A Week 72 | 505 | (463, 547] |
| | | 116A Week 84 | 589 | (547, 631] |
| | | 116A Week 96 | 673 | (631, 687] |

* Only include Day 1 post-dose measurements.

+ Weight will also be used in the threshold analysis in which the treatment baseline will be used to calculate the change; [REDACTED]

Note:

1. Visit name for analysis purpose is used to report data in tables and figures.
2. The analysis visit windows will be applied for both scheduled and unscheduled visits.
3. If no measurement is available within a visit window, the assessment will be considered missing for the visit.
4. Assessments at early treatment termination (ETT) visit will follow the windowing rules for regular visits up to 116A Week 96 if the ETT visit has a study day ≤ 687 ; otherwise, the ETT visit will be mapped into 116A Safety Follow-up (SFU) visit, if the subject doesn't have a nominal SFU visit.
5. If there is more than one measurement available within the same visit window for safety parameters, then
 - The record closest to the target day will be used.
 - If there are multiple records within the same distance from the target day, the latest record will be used.
 - SFU visit will not be windowed; instead, it will be used according to the nominal visit in relevant analyses.
6. If there is more than one measurement available within the same visit window for efficacy parameters, the record at the scheduled visit will be used. Otherwise,
 - The record closest to the target day will be used.
 - If there are multiple records within the same distance from the target day, the latest record will be used.
 - SFU visit will not be windowed; instead, it will remain as SFU.
7. [REDACTED] weight, height, and BMI assessments will be used for both efficacy and safety purposes. Their measurements will follow the visit windowing rules for efficacy parameters.

▪ **Appendix B: Standards for Safety Variable Display in TFLs**

Continuous Variables

The precision for continuous variables has been specified in the Vertex Standard Programming Rules document (Version 1.0, December 2015):

Categorical Variables: Percentages will be presented to 1 decimal place.

▪ **Appendix D: Imputation Rules for Missing Prior/Concomitant Medication Dates**

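### For children already on TEZ/IVA in the parent study, the laboratory, ECG, vital-sign and oximetry tables use a pre-TEZ/IVA baseline but count only values after the first Study 116 dose, so the parent-study treatment period is listed but not tabulated.

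*SAP*

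**What the plan says.** Several provisions act together.

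- **Baseline.** SAP 10.1 takes the last non-missing safety value "collected before the first dose of TEZ/IVA, whether the first dose was taken in the parent study or in Study 116 Part A". SAP 10.3.2 to 10.3.5 speak of a treatment baseline without defining it separately; I read it as this one.
- **Counted period.** SAP 9.1: "The safety analysis period begins at the first dose of study drug in Study 116 Part A".
- **Data used.** SAP 10.3, for everything except adverse events: "Other safety analyses will be based on data from the TE period for all subjects in the Safety Set; and will be presented overall".
- **Shift table.** SAP 10.3.2: "The threshold criterion shift from treatment baseline during the TE period will also be summarized for selected LFT laboratory parameters". SAP 10.3.5 plans a similar shift table for oxygen saturation. Several ECG, vital-sign and weight criteria in Appendix G are changes from baseline.
- **Day 1.** The footnote to the first window in SAP Table 12-1 reads "Only include Day 1 post-dose measurements", while footnote r of Protocol Table 3-1 reads "Blood samples should be collected before the first dose of study drug on Day 1". Footnotes m and o also put the ECG, vital signs and oximetry before dosing.
- **Integration.** SAP 10.1 states: "The data from Study 116 will be integrated with data from the parent studies for the purpose of providing robust safety and efficacy analyses". In SAP 10.3 the only parent-study results to be displayed are adverse events, pooled for those who received TEZ/IVA and set beside the Study 116 results with exposure-adjusted rates.

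**The concern.** The baseline and the counted period start from different doses. For a child who began TEZ/IVA in the parent study, everything measured on treatment there falls after the baseline and before the TE period, so it is on neither side of the comparison.

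Two distortions follow:

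- An abnormality that appeared and resolved in the parent study leaves no trace in the shift table.
- One that appeared there and persisted is shown as a shift during Study 116, although it arose earlier.

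The protocol foresees such children. The guidance under inclusion criterion 3 allows rollover, with approval, of children who restarted study drug after an interruption for raised transaminases.

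Long-term safety is the primary endpoint. A natural question is how many of these children ever crossed a liver or QTcF limit from their first TEZ/IVA dose onward. The planned tables cannot answer it.

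**Working it through.** **Inputs**

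- Potentially eligible: about 56 from Study 113B and 65 from Study 115 (Protocol 12.1, SAP 7.2).
- Parent-study time before rollover: 24 weeks (113B) or 8 weeks (115) (Protocol 8.1).
- Study 116 treatment: 96 weeks (SAP 4).
- Study 115 children given TEZ/IVA in the parent study: number not stated. SAP 10.4.2 limits the models to those randomised to TEZ/IVA, so not all were. I use 0 to 65 as outer bounds.

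**The plan's own figures.** 56 + 65 = 121, the total in the protocol synopsis. The Table 12-1 target days follow 7 × week + 1: Week 12 gives 85 and Week 96 gives 673. Both match, with Day 1 as the first Study 116 dose, as SAP 10.1 defines it.

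**Where each value goes, for a child treated in the parent study**

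| Value | Baseline? | TE period? | In a non-AE table? |
|---|---|---|---|
| Last before first parent-study TEZ/IVA dose | yes | no | yes, as baseline |
| On TEZ/IVA in the parent study | no | no | no |
| Day 1 panel, before the Study 116 dose | no | no | no |
| After the first Study 116 dose | no | yes | yes |

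For a Study 115 child not given TEZ/IVA there, the Day 1 panel is normally the baseline and there is no gap.

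**Illustration.** Suppose a 113B child has a normal pre-treatment ALT, 6 × ULN at parent Week 12, and normal values from Day 1 on. The shift table shows no shift. If the value is still 6 × ULN after the first Study 116 dose, the table shows a shift in Study 116. Categories defined only as multiples of ULN use no baseline; for those, the point is simply that the gap values are not counted.

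**Untabulated share of nominal treatment time per child**

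- 113B: 24 / (24 + 96) = 24/120 = 20%.
- 115, TEZ/IVA arm: 8 / (8 + 96) = 8/104 = 7.7%.
- 115, not on TEZ/IVA: 0.

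**Across the study, if all enrol and complete**

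- Study 116 time: 121 × 96 = 11,616 subject-weeks (222.6 patient-years).
- Lower bound: 56 × 24 = 1,344 subject-weeks (25.8 patient-years). 1,344 / (1,344 + 11,616) = 10.4%. Children affected: 56/121 = 46%.
- Upper bound: 1,344 + 65 × 8 = 1,864 subject-weeks (35.7 patient-years). 1,864 / (1,864 + 11,616) = 13.8%. Children affected: all 121, a limit that the Study 115 randomisation rules out in practice.

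**Pooling.** These tables are presented overall, so a change from baseline labelled Week 24 stands for nominally 24 + 24 = 48, 8 + 24 = 32, or 24 weeks since starting TEZ/IVA, depending on the child.

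**The case against.** The best defence is that the plan is coherent on its own terms. Protocol 12.3 and 12.3.1 set the same TE period and the same pre-TEZ/IVA safety baseline, so protocol and SAP do not conflict here. The tables are labelled as covering the TE period, and for that period a no-shift entry is accurate. A pre-treatment baseline is also the better choice for seeing a persistent elevation; an on-drug baseline would hide it. All of this stands. What is missing is a supplementary view; the baseline itself is not an error.

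A reader might infer more than the documents support:

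- *That the parent-study values are discarded.* SAP 10.1 puts individual data for anyone dosed in either study into listings, and the out-of-range laboratory and abnormal-ECG listings have no stated TE limit. The values are untabulated, not unused. However, the elevated-LFT listing is triggered only by a TE-period elevation, and a listing is not an incidence count.
- *That they are reported nowhere.* Protocol 9.3.1 says the parent studies were designed to evaluate safety. Their reports are not available here and may tabulate these values. Adding separate tables still cannot count each child once.
- *That no parent-study safety data are integrated.* Adverse events have a side-by-side column, and pre-treated children carry a parent-study baseline. A clinically significant laboratory finding may reach the adverse-event column, depending on the investigator's judgement. That display is not cumulative: one child can appear in both columns.
- *That a separate Day 1 panel is wasted for every child.* With same-day rollover that panel is normally the parent study's last visit, which need not be repeated. If Day 1 is delayed, it may follow time off drug.

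**Conclusion.** The point holds for Safety Set children who took TEZ/IVA in the parent study. For them, nominally 24 weeks (113B) or 8 weeks (Study 115 TEZ/IVA arm) of laboratory, ECG, vital-sign and SpO2 values enter no planned Study 116 table, despite the integration sentence in SAP 10.1. The gap is 24, 8 or 0 weeks by group, not a continuous range.

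The percentages (20% and 7.7% per child, 10.4% to 13.8% overall) are shares of nominal calendar time. They assume that all eligible children enrol, that 113B children took TEZ/IVA to Week 24, and that all complete 96 weeks. They should not be read as shares of missed events; the documents give no basis for that.

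The change is worth making because it bears on the primary safety question and uses data already to be integrated. It adds to the planned tables and does not invalidate them.

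**What to change.** - **SAP 9.1:** define a supplementary cumulative TEZ/IVA period, from the first TEZ/IVA dose in either study to the end of the Study 116 TE period. State how off-drug days between the studies are handled when Day 1 is delayed.
- **SAP 10.3.2, 10.3.3 and 10.3.5:** over that period, repeat the LFT threshold and shift tables, the ECG threshold table and the SpO2 shift table for the existing Safety Set, counting each child once. Keep the Study 116-only tables beside them.
- **SAP 10.2.5:** add matching cumulative exposure, since the planned table uses Study 116 dates only.
- **SAP 10.1:** say which tables put the integration sentence into effect.
- **Table note:** state that the cumulative tables describe children who completed the parent study and rolled over. Inclusion criterion 3 excludes those who permanently stopped study drug there, so the group is selected.

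The cost is SAP wording and a few extra runs of planned tables, with no new data collection. The drawback is that the results apply only to the rollover group. Including children who never entered Study 116 is optional and would need its own analysis set, because the Safety Set requires enrolment and a dose in Study 116.
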